6.3.1.3 Exploratory analysis

All bleeding episodes (treated or untreated)

The on-treatment and treatment policy efficacy analyses will be performed by including all bleeding episodes, regardless of administration of factor concentrates or bypassing agent infusion using the same negative binomial model as used for the primary analysis, which only includes treated bleeding episodes.

Time to first bleeding event

The time to first treated bleeding event in the treatment period will be calculated as the number of days between Day 1 and the onset date of the first treated bleeding event during the treatment period. The patient will be censored at the earlier of (Day 246, date of first intercurrent event) if no treated bleeding event has occurred. The time to first treated bleeding event in the efficacy period will be calculated similarly from Day 29 as the start of efficacy period. If a patient does not have bleeding episode data collected after Day 28 due to early study discontinuation, the time to first treated bleeding event in the efficacy period will be imputed from Day 1 as in the treatment period.

The time to first treated spontaneous bleeding event will be calculated similarly.

The proportion of patients who are bleeding free at the end of study (Month 9) will be estimated using the Kaplan-Meier method and compared using a Cox proportional hazards (PH) regression model with robust variance estimation and the treatment arm, randomization strata of number of bleeding episodes in the 6 months prior to study entry and randomization strata of hemophilia

type are treated as fixed effects . Plots of cumulative mean functions for the number of treated bleeds in the efficacy period and treatment period will be provided.

Symptoms related to bleeding

Descriptive statistics will be provided for symptoms related to bleeding events by each treatment arm.

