6.3 Efficacy analysis

Bleeding Episode Definitions

The primary source of bleeding data will be the eDiary. Additional bleeding data may be captured from the bleeding diary pages of the CRF, if not reported in the eDiary. Any other sources of bleeding data will be discussed in the CSR.

A bleeding episode is defined as any occurrence of hemorrhage that may require administration of BPA or factor. A traumatic bleeding episode is one that is caused by a known injury or trauma. Bleeding episodes sustained during sports and recreation will be counted as traumatic bleeding episodes.

Bleeding or any symptoms of bleeding at the same location that occur within 72 hours of the last injection used to treat a bleed or 72 hours after an untreated bleed at that location will be considered a part of the original bleeding event, and will count as one bleeding episode. Any bleeding symptoms that begin more than 72 hours from the last injection used to treat a bleed or 72 hours after an untreated bleed at that location will constitute a new bleeding event.

Traumatic bleeds that occur in different locations simultaneously (same date/time) in the same patient will be considered as one bleeding episode. Spontaneous bleeds that occur simultaneously (same date/time) in different locations in the same patient will be considered as separate bleeds.

Efficacy analysis will focus on observed data as collected, unless otherwise specified. Patients who discontinue study drug during the study will be strongly encouraged to continue study participation including the recording of bleeding episode data. Only bleeding episodes that are treated will be include in the primary analysis of endpoints evaluating bleeding.

Efficacy Period and Treatment Period

In the protocol, for the purpose of ABR calculation, fitusiran “Onset Period”, “Efficacy Period” and “Treatment Period” are defined. The Onset Period is defined as the first 28 days after the first dose of fitusiran, during which the AT lowering capacity of fitusiran is increasing but has not yet reached therapeutic levels. The Efficacy Period is defined as starting on Day 29 when the AT lowering capacity of fitusiran has achieved therapeutic target range. The Treatment Period is defined as the onset period plus the efficacy period. The window for each period is summarized in the table below. The corresponding window is applied to on-demand arm for analysis purpose.

	Fitusiran arm/On-demand arm

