Onset Period	Day 1 to the earlier of Day 28 and the last day of bleeding follow up
Efficacy Period	Day 29 to the earliest of (Day 246, or the last day of bleeding follow up)

Treatment Period	Onset period plus the efficacy period
------------------	---------------------------------------

The last day of bleeding follow up is defined as the deactivation date captured in eDiary.

If a patient does not have bleeding episode data collected after Day 28 due to early study discontinuation, the efficacy period will be from Day 1 to the earlier of date of study discontinuation and the last day of bleeding follow up.

The onset period, efficacy period and treatment period also exclude the period of following intercurrent events to avoid confounding of treatment effect for the primary efficacy analysis based on On-Treatment Strategy.

- After one month (28 days) from fitusiran treatment discontinuation in the fitusiran efficacy period. Excluding bleeding data after one month from fitusiran treatment discontinuation is considered reasonable and adequate considering that fitusiran is dosed monthly and EOS is one month after last dose of fitusiran.
- Perioperative period of major surgery. The perioperative period is defined as the day of the surgery through the final day on which supplemental hemostatic or antithrombotic treatments are administered as part of the perioperative treatment plan.
- Period of minor surgery is defined as the Perioperative period of surgery above or to 72 hours from the end of surgery, whichever is later.
- Period of Antithrombin treatment is defined as the first day of antithrombin treatment through the final day on which antithrombin or other anticoagulant therapies are administered plus 5 half-lives of that specific product.
- After prophylactic treatment with emicizumab, BPA or factor.

The summary statistics for number of patients who are lost-to-follow-up and who had each intercurrent event will be provided.

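### The censoring rule for the exploratory time-to-first-bleed analysis omits the end of bleeding follow-up, so read literally it carries some bleed-free leavers to Day 246

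*SAP*

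**What the plan says.** For a patient without a treated bleed, SAP 6.3.1.3 gives a two-term rule: "The patient will be censored at the earlier of (Day 246, date of first intercurrent event) if no treated bleeding event has occurred". The event is timed to "the onset date of the first treated bleeding event during the treatment period", and the efficacy-period version starts the clock at Day 29. For patients with no bleeding data after Day 28 because they left early, "the time to first treated bleeding event in the efficacy period will be imputed from Day 1 as in the treatment period". The same derivation serves treated spontaneous bleeds. The results feed a Kaplan-Meier estimate of the proportion bleed-free at Month 9 and a Cox model.

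SAP 6.3 defines the periods differently. The efficacy period runs from "Day 29 to the earliest of (Day 246, or the last day of bleeding follow up"), and the treatment period is the onset period plus the efficacy period. For patients with no data after Day 28, "the efficacy period will be from Day 1 to the earlier of date of study discontinuation and the last day of bleeding follow up".

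The intercurrent events in SAP 6.3 are major surgery, minor surgery, antithrombin treatment, prophylaxis with emicizumab, BPA or factor, and one event tied to stopping treatment: "After one month (28 days) from fitusiran treatment discontinuation in the fitusiran efficacy period". Loss to follow-up is not on the list and is reported alongside it: "The summary statistics for number of patients who are lost-to-follow-up and who had each intercurrent event will be provided". The general principle is that "Efficacy analysis will focus on observed data as collected, unless otherwise specified".

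**The concern.** Kaplan-Meier and Cox methods need a patient to leave the risk set when observation ends. The written rule does that only if an intercurrent event happens to come first. An on-demand patient who withdraws bleed-free on Day 60, with no surgery, antithrombin or prophylaxis before that, would be counted as bleed-free for a further 246 − 60 = 186 days that nobody observed.

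The on-demand arm has no discontinuation event at all. The fitusiran arm has one, but it does not reach everyone. SAP 6.3 places it in the efficacy period, so a patient who stops during the onset period arguably has none. A patient randomized to fitusiran but never dosed (a case SAP 5.5 provides for, and SAP 4 keeps in the ITT set) has no treatment to discontinue.

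At stake are the Month 9 bleed-free proportions, which would be too high, and a hazard ratio built on follow-up that was not observed and that is extended differently in the two arms.

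**Working it through.** **Text check.** Three statements govern the end of follow-up.

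| Place | End of follow-up |
|---|---|
| SAP 6.3, efficacy period | Day 246 or last day of bleeding follow-up |
| SAP 6.3, no data after Day 28 | study discontinuation or last day of bleeding follow-up |
| SAP 6.3.1.3, censoring | Day 246 or first intercurrent event |

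The third drops the follow-up term that the first two carry. For a bleed-free on-demand patient who leaves on Day 20, SAP 6.3 ends the ABR period no later than Day 20. SAP 6.3.1.3 moves the start to Day 1 and supplies no matching end. Literally, that patient contributes 246 − 1 = 245 days to the efficacy-period curve, against 246 − 29 = 217 for a completer.

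**Inputs (SAP 5.1).** ABR mean 18, SD 14 on-demand; mean 4, SD 6 fitusiran, stated for either period; 20% dropout. The plan's own total reproduces: (32 + 64)/0.8 = 120, which is 40 and 80 at 2:1. The plan gives no figure for the time-to-event analysis.

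**Assumed, not in the documents.** Leaving times uniform over the period and equal by arm; no earlier intercurrent event; gamma-distributed patient rates with exponential first-bleed times.

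**Formulae.** With T in years, k = (SD² − μ/T)/μ² and S(t) = (1 + kμt)^(−1/k). If a fraction p leaves and bleed-free leavers are carried to the end, the literal estimate is (1 − p)·S(T) + p·mean S(U), with U uniform on 0 to T.

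**On-demand, efficacy period.** T = 218/365.25 = 0.597.
- k = (196 − 18/0.597)/324 = 0.512
- S(T) = 2.58%; mean S(U) = 15.87%
- p = 5%: 0.95 × 2.58 + 0.05 × 15.87 = 3.2%
- p = 10%: 0.90 × 2.58 + 0.10 × 15.87 = 3.9%
- p = 20%: 0.80 × 2.58 + 0.20 × 15.87 = 5.2%

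At 20% that is 8 leavers × 15.87% = 1.3 of 40 patients carried.

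**Sensitivity to leaving time, p = 20%.** All in the first half (mean S = 27.3%): 0.8 × 2.58 + 0.2 × 27.3 = 7.5%. All in the second half (mean S = 4.4%): 2.9%.

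**Treatment period.** T = 246/365.25, k = 0.522: 2.2% with correct censoring, against 2.8%, 3.4% and 4.7% at 5%, 10% and 20% dropout.

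**Spontaneous bleeds, efficacy period, p = 20%.** If they are 50% of all bleeds (assumed; μ = 9, same k), 7.6% becomes 11.5%. If 75% (μ = 13.5), 4.1% becomes 7.3%.

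**Fitusiran, efficacy period.** k = 1.831 and S(T) = 39.9%. If every leaver is cut off 28 days after leaving, the 20% figure is 40.9%. If every leaver were carried to Day 246 (mean S(U) = 57.7%), it would be 0.8 × 39.9 + 0.2 × 57.7 = 43.5%. The truth under a literal reading depends on how many leavers fall outside the 28-day event.

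**Hazard ratio.** In 3,000 simulated trials of 40 against 80 (treatment term only, fitusiran leavers cut off at 28 days, efficacy period), the geometric mean was 0.237 with correct censoring and 0.258 under the literal rule at 20% dropout. The log-scale shift of 0.085 is about 0.35 of the sampling SD (0.24 to 0.25). Every simulated trial remained significant.

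**The case against.** The best defence is that the limit is already there by implication. The analysis concerns the first treated bleed within the treatment period; SAP 6.3 ends that period at last bleeding follow-up; the SAP works from observed data; and naming Kaplan-Meier implies censoring at last observation. A careful programmer would probably do the right thing. This stands as evidence of intent, and a reader should not infer that the reported analysis will be wrong. It does not repair the text: the period phrase settles which bleeds count as events, while the next sentence sets the censoring time by its own formula. Where the SAP wants last bleeding follow-up as a limit it writes it, as in SAP 6.3 and again for the Day 1 to Day 8 window in SAP 6.3.3.7.

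A second objection concerns the arms. A reader might infer that the error is confined to on-demand patients, or that 28 days bounds the fitusiran error. The documents support neither, because never-dosed patients and arguably onset-period stoppers have no such event. In an extreme case (treatment period, 20% leaving, all in the first 28 days, both arms carried) on-demand goes from 2.2% to 13.6% and fitusiran from 38.3% to 48.3%: similar inflation in both arms. The simulated hazard ratio still moves towards 1, to about 0.31, against about 0.34 if fitusiran leavers are cut off at 28 days.

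Third, SAP 6.3 uses the study discontinuation date only for patients with no data after Day 28. Adding it for everyone could make this analysis differ from the ABR periods. That is correct, and the fix below respects it.

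**Conclusion.** The omission is real as a matter of wording: the stated rule, followed exactly, credits unobserved bleed-free time. Its size is modest. With the planning rates and 20% uniform dropout, the on-demand bleed-free proportion roughly doubles in relative terms but by only 2.6 percentage points (2.6% to 5.2%). Earlier leaving or a lower event rate makes it larger; later leaving, or leavers who already had an intercurrent event, makes it smaller. No firm upper limit can be put on the fitusiran inflation.

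A reader might also suspect that the rule flatters fitusiran or reaches the main results. It does neither. In the scenarios examined the hazard ratio moves towards no effect, against fitusiran. The analysis is exploratory and outside the testing hierarchy in SAP 5.7. The ABR models take their offset from the SAP 6.3 periods, which do end at last bleeding follow-up. The leaving pattern, equal dropout by arm and the spontaneous share are assumptions; confidence is high in the missing term, not in any particular bias.

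**What to change.** In SAP 6.3.1.3, censor patients without a treated bleed at the earliest of Day 246, date of first intercurrent event and last day of bleeding follow-up. For patients with no bleeding data after Day 28, add the date of study discontinuation to that list, so that the rule matches SAP 6.3. State that it applies to all treated bleeds and to treated spontaneous bleeds, in both the treatment and efficacy periods.

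The cost is one SAP sentence and one line of derivation code. Both dates are already used in SAP 6.3, so no new data are needed.

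### Read literally, the time-to-first-bleed rule makes censoring at surgery or antithrombin treatment depend on whether the patient bleeds later

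*SAP*

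**What the plan says.** SAP 6.3.1.3 defines the time to first treated bleed in the treatment period as "the number of days between Day 1 and the onset date of the first treated bleeding event during the treatment period". It then adds: "The patient will be censored at the earlier of (Day 246, date of first intercurrent event) if no treated bleeding event has occurred". For the second version it says: "The time to first treated bleeding event in the efficacy period will be calculated similarly from Day 29 as the start of efficacy period". Time to first spontaneous bleed follows the same pattern. The output is a Kaplan-Meier bleed-free proportion at Month 9 and a Cox comparison.

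The periods come from SAP 6.3: "The onset period, efficacy period and treatment period also exclude the period of following intercurrent events". Three of the listed exclusions have an end:

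- Major surgery: "the day of the surgery through the final day on which supplemental hemostatic or antithrombotic treatments are administered" under the perioperative plan.
- Minor surgery: "Perioperative period of surgery above or to 72 hours from the end of surgery, whichever is later".
- Antithrombin: "Period of Antithrombin treatment is defined as the first day of antithrombin treatment through the final day on which antithrombin" or another anticoagulant is given, plus five half-lives of the product.

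Two have no end: time beyond 28 days after fitusiran discontinuation, and time after prophylaxis starts. The SAP does not define the date of an intercurrent event. The period table in 6.3 also ends each period at the last day of bleeding follow-up, a limit that the censoring sentence leaves out.

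**The concern.** Once a surgery or antithrombin window closes, follow-up belongs to the period again. Take two patients with minor surgery on Day 60. One has a first treated bleed on Day 150, which lies in the treatment period and is an event at Day 150. The other never bleeds and is censored at Day 60. Follow-up after surgery is used only for the patient who bleeds. Kaplan-Meier and Cox both assume that censoring carries no information about the later outcome, and here it does.

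At stake are the Month 9 bleed-free proportion, which is an easily quoted measure of benefit, and the reproducibility of the curve. The sentence can be programmed in more than one way.

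**Working it through.** **The plan's own figure.** The documents give no number for this analysis. The planning figure nearest to it, in SAP 5.1, reproduces. With dispersion k = (SD² − mean/t)/mean² and t = 1 year, k = (196 − 18)/324 = 0.549 on demand and (36 − 4)/16 = 2.0 on fitusiran. The variance of the log rate ratio is (1/18 + 0.549)/32 + (1/4 + 2.0)/64 = 0.054, so the standard error is 0.233. Since |ln(4/18)| = 1.504, power exceeds 99.9%. Other choices of t and a common k give at least 99.8%. The stated power above 90% holds, and so does 96/0.8 = 120.

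**True bleed-free proportion.** Under the same gamma-Poisson model, P(no bleed) = (1 + k·mean·t)^(−1/k).

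- Fitusiran, Day 29 to 246 (218 days, t = 0.597): k = 1.831, P = 5.37^(−0.546) = 39.9%.
- Fitusiran, 246 days (t = 0.674): k = 1.879, P = 6.06^(−0.532) = 38.3%.
- On demand: 2.6% over 218 days and 2.2% over 246 days.

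**Literal rule.** Assume a share p of patients has one temporary event at a uniformly distributed time. At day d the literal rule has removed only those who stay bleed-free to the end T and whose event came before d, a fraction p·S(T)·d/T. All bleeds are kept. The hazard that Kaplan-Meier estimates is therefore f(d)/[S(d) − p·S(T)·d/T], which is larger than the true f(d)/S(d). The table sets a simulation (400,000 patients per setting, 7-day window) beside this formula, which ignores the window.

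| Share with a temporary event | Efficacy period, simulated (true about 39.9%) | Efficacy period, formula | Treatment period, simulated (true about 38.3%) |
|---|---|---|---|
| 5% | 39.5% | 39.4% | 37.7% |
| 10% | 38.8% | 38.8% | 37.3% |
| 20% | 37.6% | 37.6% | 36.2% |
| 30% | 36.5% | 36.3% | 34.9% |

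In the on-demand arm the fall is 0.1 to 0.5 points. Two consistent rules recover the truth in the efficacy period (39.8% to 40.1% throughout): censoring every patient at the first intercurrent event, and removing only the window.

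**Permanent exclusions.** After prophylaxis no later bleed counts for anyone, and the simulated bias is nil. For fitusiran discontinuation only bleeds within 28 days of stopping can still count. If the event is dated at stopping, the bias is −0.2, −0.4 and −0.8 points at 5, 10 and 20% discontinuing. If it is dated at day +28, there is none.

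**The opposite push.** A bleed-free patient who withdraws without a listed intercurrent event is carried to Day 246. With 5, 10 and 20% such withdrawals at uniform times and no temporary events, the fitusiran proportion rises from about 40% to 40.9, 41.7 and 43.6%, and the on-demand proportion from about 2.6% to 3.3, 3.9 and 5.2%. With 20% withdrawal and 20% temporary events at fitusiran rates the result is 41.4% against a true 39.8%. With 5% withdrawal and 20% temporary events it is 38.6% against 40.0%. The sign can go either way.

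**Day 29 origin.** Nothing limits the intercurrent event to Day 29 or later. A patient with no efficacy-period bleed and an onset-period event is censored before time zero. If events are uniform over the treatment period, 28/246 = 11% of events (not of patients) fall there.

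**The case against.** The censoring sentence can be read as ordinary survival wording: censor at that date if no bleed has happened by then. That reading is fair, and it removes the bias. A reader might go further and infer that both readings fail. The documents do not support this. Stopping a first-event analysis at the first intercurrent event is legitimate and, in the check above, unbiased. Its cost is that a minor-surgery window that may last only about 72 hours ends follow-up that the primary analysis keeps. What stands is that the SAP does not say which reading applies.

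Two other stronger inferences are tempting. One is that every intercurrent event produces the asymmetry. It does not, because prophylaxis is excluded permanently for everyone and discontinuation matters only through its 28-day tail. The other is that the reported bleed-free proportion will be too low. That is the direction of this mechanism alone, and the missing end of bleeding follow-up can outweigh it.

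The size is also likely to be small. Anticipated or planned surgery is an exclusion criterion (protocol 5.2), non-urgent surgery must not be scheduled (4.1), and non-urgent major surgery should be postponed (6.6). Minor procedures do remain possible with dosing uninterrupted. At 5% the shift is about 0.5 points, or 0.4 of a patient among 80. The binomial standard error at 38.3% with 80 patients is √(0.383 × 0.617/80) = 5.4 points. No effect on the hazard ratio has been computed. On the Day 29 point, the efficacy-period sentence could be taken to cover only events from Day 29 on, but it does not say so.

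**Conclusion.** The point holds for temporary intercurrent events under the literal text: surgery and antithrombin treatment censor only patients who do not bleed later. By itself this lowers the fitusiran bleed-free proportion by about 0.5 to 1 point at 5-10% of patients affected, and by about 2 to 3.5 points at 20-30%. The result rests on the SAP's planning means and SDs, a gamma-Poisson model, uniform event times and assumed frequencies, of which the lower are more plausible. The net bias of the whole rule is not established. The alternative reading is unbiased but discards usable follow-up, and on either reading the efficacy-period version needs a rule for onset-period events. The analysis is exploratory and outside the testing hierarchy in SAP 5.7. The primary negative binomial analysis removes bleeds and matching time together, so it is unaffected. Severity is minor.

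**What to change.** State in SAP 6.3.1.3 one rule that does not depend on later bleeds.

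- Preferred: take only the excluded days of temporary events out of the risk set (start-stop intervals), as the primary analysis does. Censor every patient still without an event at the earliest of Day 246, the last day of bleeding follow-up, and the start of a permanent exclusion (28 days after fitusiran discontinuation, or start of prophylaxis).
- Alternative: censor every patient without an earlier bleed at the first intercurrent event, ignore all later bleeds, and add the last day of bleeding follow-up to the censoring times.
- In either case, define the date of each intercurrent event. For discontinuation, say whether it is the stop date or day +28.
- For the efficacy-period version: ignore temporary windows that close before Day 29, start risk after any window that spans Day 29, and give no efficacy-period risk time to patients whose permanent exclusion began before Day 29.

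The cost is a few SAP sentences and start-stop data coding before database lock. No new data are needed.
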